10.3. Data Collection

For eligible cases, clinical data related to the TIPS procedure will be extracted from the medical records and captured into a Data Collection Tool by trained study staff:

Electronic medical records (Epic, Verona, Wisconsin) and the picture archiving and communication system (PACS) database will be reviewed for patient demographic data, applicable TIPS datapoints, and the primary Argon device used for TIPS procedure. Complications will be categorized according to the Society of Interventional Radiology Quality Improvement guidelines.¹⁰

10.3.1. Baseline Information

Demographics including age, sex, height, weight, race, and ethnicity will be captured. BMI will be calculated using the patient's height and weight. Initial indication for TIPS plus MELD and Child-Pugh Score will be collected. Standard-of-Care imaging will be reviewed.

10.3.2. Procedural Information

The information of each eligible case that has gone under the TIPS procedure will be captured. Information such as the following will be collected and recorded:

- Procedure date
- Scorpion® Portal Vein Access Set or Scorpion®X Portal Vein Access Set Used
- Jugular access site
- Sheath used
- Imaging used
- Fluoroscopy time
- Radiation dosage measured in Air kerma (mGy)
- Contrast volume used
- Portal vein access (PVA) time
- Hepatic vein used for access
- Portal vein access site
- Pressure gradient measurements: pre- and post-delivery of stent
- Stent used and stent count
- Presence of residual varices
- Procedure duration
- Technical success
- Procedural success
- Length of hospital stay
- Number of ICU days
- AE assessment

10.3.3. Follow up Information

Follow up information will be collected within 30 days post-procedure. Information such as the following will be collected and recorded:

- Follow up visit date
- MELD and Child-Pugh Score
- Patency assessment
- Clinical assessment including status and evaluation for encephalopathy
- Clinical improvement (Yes, No, Unknown)
- AE assessment

Standard-of-Care imaging (e.g. Doppler Ultrasound) will be reviewed for TIPS patency, if available.

11. ADVERSE EVENTS, ADVERSE DEVICE EFFECTS, AND DEVICE DEFICIENCIES

11.1. Definitions

An adverse event (AE) is defined as any undesirable clinical occurrence or change from the patient's baseline condition, whether it is considered device related or not.

A serious adverse event (SAE) is defined as any untoward/undesirable adverse experience that results in any of the following outcomes:

- a) Death
- b) A life-threatening illness or injury
- c) Inpatient or prolonged hospitalization
- d) A permanent impairment of a body structure or a body function
- e) Medical or surgical intervention to prevent life-threatening illness or injury or permanent impairment to a body structure or a body function
- f) Congenital abnormality or birth defect

An adverse device effect (ADE) is an adverse event that, when in the judgement of the Investigator has a reasonable time sequence associated with use of the device and it is believed that the device directly caused or contributed to the adverse event.

A device deficiency is defined as an inadequacy of the medical device related to its identity, quality, durability, safety or performance, such as malfunction, misuse or use error and inadequate labeling.

11.2. Reporting

This investigation is performed using marketed product thus requiring reporting of device-related serious adverse events and deficiencies to the manufacturer via Argon's policy and procedures for complaints and issues handling which is implemented for all products as part of our mandated post market vigilance. Due to the retrospective approach, incidents may have already been reported as part of the hospital's routine.

The collection of adverse events in this study will be limited due to the retrospective nature of the design. Adverse events that will be captured in this study are those believed to be consistent with commercially available TIPS devices. As such, only procedure-related complications will be captured from the medical records and recorded in the study database which may occur at any time during the procedure or within 30 days following the procedure.

Each adverse event will be assessed by the Investigator for severity, seriousness, relationship to the device/procedure, action taken, and outcome. Events will be categorized as defined per Society of Interventional Radiology guidelines.¹⁰

Table 4. SIR Standards of Practice Committee Classification of Complications by Outcome

Minor Complications	A. No therapy, no consequence. B. Nominal therapy, no consequence; includes overnight admission for observation only.
Major Complications	C. Require therapy, minor hospitalization (< 48 hours). D. Require major therapy, unplanned increase in level of care, prolonged hospitalization (> 48 hours). E. Permanent adverse sequelae F. Death

11.3. Procedure-related Complications

Based on state of the art for TIPS procedures and similar devices, the following adverse events may be considered procedure-related complications:

- Hepatic encephalopathy
- Infection/Sepsis
- Liver failure
- Contrast induced nephropathy
- Allergic reaction to contrast utilized intra-procedurally
- Adverse reactions associated with administration of general anesthesia or conscious sedation
- Death

12. STATISTICAL CONSIDERATIONS

12.1. General

All data processing, analyses, and reporting will be performed by an independent biostatistician who otherwise is not involved in the chart review or data collection. The analysis will be conducted using SAS (PC Version 9.4 or higher).

12.2. Sample Size Determination

No formal sample size calculation was performed. All eligible cases will be enrolled in the study. Per preliminary estimation and historical sales report, we anticipate that there will be at least 50 cases for this study at 1 clinical site in the US.

12.3. Analysis Population

Due to the nature of this retrospective study, all eligible cases will be analyzed for safety and effectiveness on an 'as-treated' basis.

12.4. Statistical Analyses

Unless otherwise specified, for continuous variables, descriptive statistics will include the number of patients/procedures, mean, standard deviation, median, minimum, and maximum values. Categorical variables will be summarized using frequency and percentages. All comparative tests are 2-sided with the confidence level set to 95%.

Given the retrospective nature of this protocol, there may be missing or incomplete data, thus not all may be available for all patients. Unless otherwise stated, missing data will be handled as it is, except for dates that are required for calculating event time, the partial dates will have either '01' or 'Jan' imputed with an exception for dates related to the event where the date closest to the last event (visit date, procedure date, etc.) should be used rather than arbitrary '01' of that month and year.

The analytical unit is TIPS procedure. No formal statistical hypothesis will be tested for this single-arm study.

Sub-group analysis (e.g. by gender, age group, or Portal Vein Access Set type) may be conducted if the sample size in each subgroup is sufficient. Student's t-test will be employed for continuous variables and Pearson's chi-square test for categorical variables.

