Population	
All patients who underwent a TIPS procedure between February 1, 2022, and February 29, 2024 will be considered for enrollment in the study. Procedural data will be collected from patient medical records through hospital discharge.
 
Each TIPS procedure that was completed using one of the Scorpion Portal Vein Access Kits will be considered as an individual case. Cases that meet all inclusion criteria and do not meet any exclusion criteria will be considered eligible for enrollment.

Inclusion Criteria	
 1. Scorpion or Scorpion X kit introduced into the vasculature as the initial device for portal vein access.
Exclusion Criteria	
 1. TIPS procedure was not initiated and/or no portion of the kit was introduced into the vasculature. 2. Inaccessible medical records.
Statistical Analysis	
Statistical Methodology	
Patient demographics and performance parameters will be summarized with mean, standard deviation, median, and range for continuous variables and with frequencies and percentages for discrete variables. Sub-group analysis will be conducted when sample size permits.

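### Section 12.4 plans only counts and percentages for the two primary proportions; exact 95% intervals, with the safety numerator and denominator defined per case, should be added

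*Combined protocol and SAP*

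**What the plan says.** Section 12.4 gives one rule for all categorical outcomes: "Categorical variables will be summarized using frequency and percentages". The synopsis matches it, "with frequencies and percentages for discrete variables". Neither place, nor any other section, plans an interval for a proportion.

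The only 95% level is in the sentence "All comparative tests are 2-sided with the confidence level set to 95" percent. It concerns comparative tests, which in a single-arm study can only be the optional subgroup comparisons. The same section adds that "No formal statistical hypothesis will be tested for this single-arm study".

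Section 9.1 makes technical success the primary effectiveness endpoint and a composite of major complications the primary safety endpoint. Section 12.2 reports no sample size calculation, enrolls every eligible case and anticipates a minimum of 50. Section 4.3 says that the study will supply clinical data for an initial CE Mark application, and that its findings are meant to show that the sets keep up with the state of the art and satisfy the sponsor's acceptance criteria.

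On counting, "The analytical unit is TIPS procedure", and section 10.2 gives each attempt its own case number. Section 11.2 captures procedure-related complications up to 30 days. Section 7.1.2 defines the incidence of procedural complications as a total of occurrences.

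**The concern.** With no test and no precision target, the estimate and its uncertainty are all the evidence that this study offers on its primary endpoints. The plan presents only the estimate. A result such as 1/50 (2%) or 50/50 (100%) would stand alone, although section 4.3 wants it set against an external standard. That comparison is about the device and not only about the cases at this one site, so enrolling every eligible case does not remove the sampling uncertainty.

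A second gap affects whether the uncertainty can be worked out at all. Section 9.1 does not say that the safety numerator is the number of cases with at least one major complication, and the definition in section 7.1.2 reads as an event count. Section 12.4 leaves missing data as they are, so the denominator for an endpoint followed to 30 days is not fixed either. A binomial interval is valid only when each case contributes one yes or no.

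**Working it through.** The plan has no calculated figure to reproduce: the 50 in section 12.2 comes from a preliminary estimate and a sales report.

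**Inputs.** N = 50 is the anticipated minimum (sections 8.1 and 12.2). N = 75 and N = 100 are assumptions that show the effect of a larger yield. The documents give no expected rate for either primary endpoint at this site, so the observed counts x are assumptions too, shown as a range. Every case is assumed to be fully observed and independent of the others.

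**Formula.** Two-sided 95% Clopper-Pearson limits from beta quantiles:
- lower = Beta(0.025; x, N − x + 1), taken as 0 when x = 0
- upper = Beta(0.975; x + 1, N − x), taken as 1 when x = N

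With no events, the upper limit reduces to 1 − 0.025^(1/N). At N = 50 this is 1 − 0.025^(0.02) = 7.1%. Limits for success mirror those for failures: 50/50 has a lower limit of 100 − 7.1 = 92.9%.

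**Results at N = 50.**

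| Major complications | Exact 95% limits | Technical success | Exact 95% limits |
|---|---|---|---|
| 0/50 (0%) | 0 to 7.1% | 50/50 (100%) | 92.9 to 100% |
| 1/50 (2%) | 0.05 to 10.6% | 49/50 (98%) | 89.4 to 99.9% |
| 2/50 (4%) | 0.5 to 13.7% | 48/50 (96%) | 86.3 to 99.5% |

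**Results at larger N.**

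| N | Upper limit, 0 events | Upper limit, 1 event | Lower limit, all successes | Lower limit, 1 failure |
|---|---|---|---|---|
| 75 | 4.8% | 7.2% | 95.2% | 92.8% |
| 100 | 3.6% | 5.4% | 96.4% | 94.6% |

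**How easily a low count arises.** P(X ≤ 1) = (1 − p)^50 + 50p(1 − p)^49. If the true major complication rate were 5% (an assumption), this is 0.077 + 0.202 = 0.279. At 7% (also an assumption) it is 0.027 + 0.100 = 0.126 after rounding. So 0 or 1 events in 50 would be seen 28% or 13% of the time.

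**Choice of method.** Wilson limits at N = 50 differ from the exact ones by about 1 point or less (for 1/50, an upper limit of 10.5% against 10.6%), so the method does not drive the result.

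**The case against.** The strongest reply is that this is close to a reporting preference. The study is openly descriptive, counts will be published, and an exact interval is a fixed function of x and N that any reader can compute or the sponsor can add later. Nothing is biased and no data are lost. Section 4.3 is rationale and not a decision rule. The acceptance criteria are not in these documents, so one cannot tell whether they apply to point estimates or to limits, or whether another document already requires intervals. The plan sets no precision target, so wide is a judgement, and 50 is the least favourable N if the forecast is met.

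Most of this stands, and it limits the point to presentation and definition. It does not remove the point. Readers can recover the safety interval only if the published count is of cases and the denominator is clear, and the plan secures neither. Prespecifying the interval also prevents a later choice of whether, and by which method, to show uncertainty.

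A reader might infer that the study cannot support its intended use, or would fail its criteria. The documents do not support that, because the criteria's values are not given. A reader might also set the 7.1% upper limit for 0/50 against the 3.6% cited in section 4.2. That figure is for portal vein puncture-related complications with another manufacturer's sets, a different endpoint, and is no benchmark for the major complication composite.

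**Conclusion.** The point holds as an omission in how the primary results are presented and defined. It is not a flaw that invalidates the descriptive design. At 50 cases, an observed major complication rate of 2% (1/50) is compatible with a true rate of up to 10.6%, about five times as high (10.6/2 = 5.3). A perfect technical success record is compatible with a true rate as low as 92.9%. At 100 cases the uncertainty is smaller but still worth showing: an upper limit of 3.6% with no events and a lower limit of 96.4% with 100/100.

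These figures rest on assumed counts, complete observation of every case, one yes or no per case, and independent cases. The last assumption is only approximate if patients contribute more than one procedure, and the documents do not say how many do. Whether the limits would change a conclusion against the acceptance criteria cannot be judged from the documents.

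**What to change.** In section 12.4, and in matching words in the synopsis:

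- Report technical success and major complications as n/N, percentage and two-sided 95% Clopper-Pearson interval.
- For safety, define n as the number of cases with at least one major complication, not the number of events. Define N as the number of eligible cases, and show how many of them lack 30-day information.
- Show the interval beside any statement that the sets match the state of the art or meet the acceptance criteria.
- Report how many patients contribute more than one case. If any do, repeat the interval using each patient's first case only.

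The cost is a few sentences of SAP wording and standard options in the SAS software already named in section 12.1. No extra data are needed beyond linking cases to patients, which the site's patient log should allow. The downside is that the intervals will look wide, especially if the yield is close to 50.

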4.2. Prior Investigations

The Rosch-Uchida and Colapinto sets manufactured by Cook Medical (Bloomington, Indiana, US) are two different needle sets currently available and most encountered. A recent systematic review of literature showed that the overall incidence of PVPC with the Cook sets was 3.6%.⁶ The procedure duration varies in literature due to protocol differences and imaging techniques used. David et al.⁷ reported a mean procedure duration of 86.2 minutes using ultrasound guidance. In a study evaluating time to portal vein access, mean time to portal venous access was statistically significant between conventional fluoroscopy at 46 minutes and intravascular US-guided TIPS at 31 minutes.⁸

In a retrospective study of 15 cases with Scorpion X (Needle model), technical success was achieved in 100% of cases with an average of 2.7 passes, and because of the bi-directional needle, no cases required adjustment to the curvature of the needle.⁹

The APASS prospective study had three cases, but the study was early terminated due to slow enrollment accrual. Two cases were Scorpion, while the remaining one was Cook. Procedural success was achieved in 100% of cases.

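### Section 12.4 fixes Pearson's chi-square for categorical subgroup tests with no provision for very sparse tables; a lone event in a subgroup of about 20% or less then gives p<0.05 (minor)

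*Combined protocol and SAP*

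**What the plan says.** Section 12.4 (Statistical Analyses) specifies Student's t-test for continuous variables and "Pearson's chi-square test for categorical variables" in its subgroup paragraph. It gives sex, age group and access set type as example subgroups. On level, it says: "All comparative tests are 2-sided with the confidence level set to 95" per cent, read here as a two-sided 5% test. The same section also says: "No formal statistical hypothesis will be tested for this single-arm study".

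The condition for doing subgroup analysis is that it "may be conducted if the sample size in each subgroup is sufficient". The Synopsis (section 3) puts it as: "Sub-group analysis will be conducted when sample size permits". Neither gives a number, and neither refers to events or expected cell counts. No exact test, continuity correction or expected-count rule appears anywhere in the document.

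Section 12.2 expects at least 50 cases, and section 12.4 makes the procedure the unit of analysis. Section 5.1 does not require equal use of the two models, so an uneven split by set type is possible. No split is given.

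**The concern.** Pearson's chi-square relies on a large-sample approximation that is poor when expected counts are very small. Some endpoints here may be that rare. Section 4.2 reports, for 15 earlier Scorpion X cases, that "technical success was achieved in 100% of cases with an average of 2.7 passes". If technical failure is equally uncommon in this study, a subgroup comparison of the primary effectiveness endpoint could rest on one event.

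At stake is a misleading subgroup p-value, not the main result. Section 4.3 says the data will support an initial CE Mark application, and section 5.1 states that the choice of stylet or needle will not affect the endpoints. One technical failure in the less-used set could be reported as p<0.05 and appear to contradict that statement, on evidence to which an exact test gives p=0.20.

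**Working it through.** The plan has no figure of its own to reproduce, since section 12.2 says no formal sample size calculation was done.

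**Inputs.** From the documents: uncorrected Pearson, two-sided 5%, at least 50 cases. Assumed: the subgroup splits and the event rates. The 3.6% rate is borrowed from section 4.2, where "the overall incidence of PVPC with the Cook sets was 3.6" per cent. That is a puncture-related rate with comparator sets, so rates from 1% to 30% were also examined.

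**One event in total, in a subgroup of m out of N cases.** Pearson's statistic reduces to N(N−m)/[m(N−1)], to be compared with 3.84. Fisher's two-sided p is m/N when the subgroup is the minority.

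- N=50, m=10: 50×40/(10×49) = 4.08, p=0.043; Fisher 10/50 = 0.20.
- N=50, m=11: 50×39/(11×49) = 3.62, p=0.057; Fisher 0.22.
- N=100, m=20: 100×80/(20×99) = 4.04, p=0.044; Fisher 0.20.

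Setting the statistic to 3.8415 gives a threshold share of 1/(1 + 3.8415×49/50) = 21.0% at N=50, and 1/(1 + 3.8415) = 20.7% for large N. Hence the threshold of about 20% or less.

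**Other sparse tables.**

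| Table | Pearson p | Fisher p | Smallest expected count |
|---|---|---|---|
| 1/40 v 1/10 | 0.28 | 0.36 | 2×10/50 = 0.4 |
| 1/40 v 2/10 | 0.037 | 0.098 | 3×10/50 = 0.6 |
| 0/35 v 2/15 | 0.027 | 0.086 | 2×15/50 = 0.6 |

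So one event in each subgroup does not trigger the problem.

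**How often a lone event misleads.** With a 40/10 split and no true difference, the chance of exactly one event, falling in the 10, is 10p(1−p)^49. This is 6.1%, 7.4%, 6.0% and 4.0% at rates of 1%, 2%, 3.6% and 5%. Given exactly one event, Pearson rejects 10/50 = 20% of the time; Fisher never does.

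**Type I error.** This is the sum of the probabilities of all tables with p≤0.05, from two binomials with a common rate.

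- Pearson, N=50, rate 3.6%: 4.2% at subgroup size 5; 5.2%, 6.1%, 6.6%, 7.7% and 8.9% at sizes 6 to 10; 1.75% at 11; at most 3.8% from 11 to 25. At size 10, about 6.0 of the 8.9 points come from the lone-event table, which drops out at 11. Sizes 3 and 4 (8.0% and 7.2%) are left out as unlikely to count as sufficient.
- Pearson, N=50, rates 10% to 30%, sizes 5 to 25: 3.2% to 5.8%.
- Pearson, 80/20, rates 1%, 2%, 3.6%, 5%: 8.8%, 8.7%, 6.3%, 4.7%.

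**Two fallback rules, N=50, sizes 5 to 25.**

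- Fisher when any expected count is below 5: at most 1.9% at rates of 1% to 5%; 1.0% to 2.5% at 10%.
- Fisher when the smallest expected count is below 1: at most 2.8% at rates of 1% to 5%; at most 4.9% at 10% (the maximum is at 25/25). At 15% to 30% its maximum equals Pearson's, up to 5.8%.

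Power for true rates of 5% v 30%, with the higher rate in the smaller subgroup:

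| Split | Pearson | Below-1 rule | Below-5 rule |
|---|---|---|---|
| 40/10 | 64% | 56% | 55% |
| 35/15 | 72% | 71% | 59% |
| 25/25 | 71% | 71% | 61% |

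**The case against.** The case against acting is that the trigger is narrow. The clearest failure needs optional tests to be run on a rare endpoint, with a single event, in a minority of about 20% or less, and the documents show neither that split nor that rate. At 3.6% Pearson is conservative at every subgroup size from 11 to 25. All the exceedances at N=50 are in subgroups of 10 or fewer, which a sensible reading of "sufficient" might exclude. An independent biostatistician runs the analysis (section 12.1) and could choose an exact test unprompted. Replacing Pearson too readily also loses power to see a real subgroup difference.

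Most of this stands and limits the weight of the point. It does not remove it. A gate on size does not look at events: 20 of 100 cases could pass it and one event there still gives 0.044, although that needs twice the stated minimum number of cases. An unprompted change of test would be a departure from the written plan. The power argument bears on which fix to choose.

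A reader might infer more than the documents support:

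- *That the subgroup tests are anti-conservative in general.* The enumeration shows otherwise.
- *That any sparse event in a small subgroup gives p<0.05.* 1/40 v 1/10 gives 0.28.
- *That 3.6% is this study's expected complication rate.* It is a puncture-related rate for other sets. Section 11.3 says "the following adverse events may be considered procedure-related complications" and lists encephalopathy, infection, liver failure and death, so total complications need not be rare.
- *That the primary conclusions are at risk.* They are descriptive and use no test.

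**Conclusion.** The point holds as a minor one, to consider. Section 12.4 prescribes a test that gives a misleading p-value in an identifiable kind of table, and nothing in the plan diverts that table to another method. The size is 0.043 against 0.20 for a lone event at 40/10. Type I error reaches at most 8.9% in 50 cases at 3.6%, within a narrow band of subgroup sizes. These figures rest on uncorrected Pearson at two-sided 5%, on assumed splits and rates, and on the tests actually being run. The concern fits a rare binary endpoint such as technical failure.

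**What to change.** In section 12.4, replace the chi-square provision with a statement that categorical subgroup results will be shown as counts and percentages with exact (Clopper-Pearson) 95% confidence intervals and without p-values. This suits a study that tests no formal hypothesis, and it shows the uncertainty plainly: 1/10 is 10% with an interval of 0.3% to 44.5%, and 0/40 is 0% with an interval of 0% to 8.8%.

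If p-values are kept, specify Fisher's exact test when the smallest expected count is below 1 and Pearson's chi-square otherwise. Every sparse table shown above would then go to Fisher. The usual below-5 threshold is not recommended as the main rule. In 50 cases it leaves Pearson in use only with 10 to 40 events at 25/25, 17 to 33 at 35/15 and exactly 25 at 40/10, and it costs about 10 to 13 points of power at 25/25 and 35/15. The below-1 rule avoids most of that loss, though at 40/10 it gains almost nothing (56% v 55%).

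The cost is one or two sentences and a routine option in SAS, with no change to data collection. The downside is fewer nominal subgroup signals from sparse tables and, if p-values are dropped, no formal comparison between subgroups on categorical outcomes.
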